We hypothesize that administration of TXA will reduce perioperative bleeding in osteotomy procedure with minimal side effects. As a result, swelling and postoperative pain will decrease thus improving postoperative outcomes. While TXA has been used in various orthopedic surgeries to reduce bleeding, no study has investigated the efficacy of TXA during a TTO procedure and TXA during HTOs have limited available studies. The available literature shows perioperative bleeding and hematoma significantly decreased during HTO procedures³. By comparing high tibial osteotomy patients to tibial tubercle osteotomy patients, we will determine if there is a difference in efficacy or if both cohorts will be similarly affected.

Study Design

This is a single-center, prospective cohort study. Patients will be assigned to their cohorts based on diagnosis and appropriate treatment as determined by the surgeon. Patients will be consented in the study once they are scheduled for either a HTO or TTO, therefore this will not be a randomized study. The study is comparing blood loss and postoperative pain after TXA administration in patients receiving a high tibial osteotomy (HTO) to patients receiving a tibial tubercle osteotomy (TTO) with or without medial patello-femoral ligament (MPFL) reconstruction. One gram of intravenous tranexamic acid will be administered before tourniquet inflation and 1 gram of IV TXA before closure of the incision. Patients will be asked on postoperative day 1, 2 and 7 to rate their pain according to the VAS scale. Patients will have their knee swelling measured immediately postoperatively and at their one-week follow up visit. The swelling ratio is defined as the postoperative mean circumference of upper pole of patella and lower pole of patella divided by the preoperative values.

Primary Objective

The primary objective of the study is to determine if there are any differences in blood loss between patients undergoing high tibial osteotomy (HTO) and tibial tubercle osteotomy (TTO) with or without medial patello-femoral ligament (MPFL) reconstruction.

Secondary Objective

Secondary objective of the study is to determine if there is a difference in post operative pain and swelling between patients undergoing HTO compared to patients undergoing TTO.

II. CHARACTERISTICS OF THE RESEARCH POPULATION

Number of Subjects

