Patients indicated and scheduled for a high tibial osteotomy or tibial tubercle osteotomy with or without medial patello-femoral ligament reconstruction will be identified from faculty surgeon case logs at the NYU Langone Health, Langone Orthopedic Hospital Sports Medicine Division. After informed consent is obtained, a chart review of patients' medications and past medical histories will be reviewed based on their electronic medical records to identify any current pain medications or exclusion criteria. Patients will be in the study for 1 week, until their first follow up visit.

Patients will be given 1 gram of intravenous tranexamic acid (TXA) before tourniquet inflation and 1 gram of IV TXA before closure of the incision. Immediate post-operative management will not be affected by this study. The study team will not be blinded to the study as there is no randomization to each cohort. All patients will receive a standardized regimen of aspirin for DVT prophylaxis and Percocet for pain management, which is standard of care post-operative treatment.

Information to be recorded pre-operatively includes age, sex, height, weight, BMI, and American Society of Anesthesiology (ASA) classification. Intra-operative information will also be recorded, including operative time, and estimated blood loss. During the surgery, a suction device is utilized to remove excess blood from the surgical site and sucked into the suction drain and placed into a measuring cup. We will measure the perioperative blood loss by look at the measuring cup and seeing how much blood is inside. Knee swelling postoperatively will be measured using the swelling ratio. The swelling ratio was defined as the circumference of the operative limb divided by the circumference of the contralateral limb. Pain severity scores at rest will be assessed by use of a visual analog scale (VAS; 0 = no pain, 10 = worst pain imaginable) at 0.5, 1, 1.5, 2, 4, 6, 24, and 48 hours as well as 7 days after surgery. Percocet consumption will be recorded at 24 hours, 1 day, 2 days and 7 days after surgery. Incidence of TXA-related side effects (nausea/vomiting, itching, anxiety, increased thirst, rapid heartbeat) in the first 24 hours will be noted. Time to discharge from the post-anesthesia care unit (PACU) and time to discharge from the hospital will be recorded.

Analysis and Data Monitoring

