Data monitoring will be done by [name], the principal investigator. He will review the following accumulated data quarterly.

He will monitor whether or not:

1. Collection and storage of patient data was performed in a sensitive and secure manner, as defined in the informed consent form and protocol, ensuring information is stored on REDCap.
2. All study activities were conducted with primary emphasis on patient care and wellbeing, ensuring the patients are not in discomfort and have an abnormally high VAS following the surgery.
3. If there were any adverse events, and if so were addressed appropriately and per protocol
4. The risk/benefit to patients has remained the same throughout the course of the study.

The study will be stopped if there are unexpected severe AE's in more than one patient. Adverse events will be defined as negative reactions to the intravenous TXA during or after surgery, including seizures, vision problems. We will submit summaries of data and safety monitoring annually.

Data Analysis

According to a post hoc power analysis calculating the effect size using our preliminary data, >15 patients are required with $d=0.6$ to obtain a power of 0.80 and an alpha value of 0.05. Therefore we are including an additional 5 patients per group to account for patients that may be

lost to follow up. Statistical analysis will be performed using chi-squared and/or fisher's exact testing depending on size for binary variables. Continuous variables will be compared with paired t-tests if the data is approximately normally distributed. If the data is not normally distributed, Mann-Whitney tests will be used. All protected health information will be removed prior to statistical analysis. We will use patient subjective pain, perioperative blood loss and knee swelling data as statistical endpoints. Subjective pain will be measured with the VAS (visual analogue scale), perioperative blood loss will be measured looking at blood loss from the suction drain after surgery. The swelling ratio is defined as the postoperative mean circumference of upper pole of patella and lower pole of patella divided by the preoperative values according to our previous study. The endpoints must be statistically significant between the two cohorts to show TXA is effective.

Data Storage and Confidentiality

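### Pain is scored at up to nine times, listed differently in two sections, and the analysis plan names only a separate simple test per variable, so there is no single defined pain result

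*Combined protocol and SAP*

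**What the plan says.** Four places in the combined protocol and SAP bear on this.

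- **Schedule in section III, Methods and Procedures:** pain at rest on a 0 to 10 visual analogue scale (VAS) is scored "at 0.5, 1, 1.5, 2, 4, 6, 24, and 48 hours as well as 7 days after surgery". That is nine scores per patient.
- **Schedule in section I, Study Design:** "Patients will be asked on postoperative day 1, 2 and 7 to rate their pain according to the VAS scale". That is three.
- **Role of pain:** it is a secondary objective in section I ("Secondary objective of the study is to determine if there is a difference in post operative pain and swelling"). It is also one of three endpoint domains in Data Analysis: "We will use patient subjective pain, perioperative blood loss and knee swelling data as statistical endpoints".
- **Analysis in section III, Data Analysis:** "Continuous variables will be compared with paired t-tests if the data is approximately normally distributed", and otherwise "If the data is not normally distributed, Mann-Whitney tests will be used". The section closes with a decision rule: "The endpoints must be statistically significant between the two cohorts to show TXA is effective".

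Data Analysis defines the pain endpoint by its instrument alone. It gives no time point, mean, peak, area under the curve, repeated-measures model or adjustment for several tests.

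**The concern.** A t-test or Mann-Whitney test takes one number per patient. With nine scores per patient, the plan has to choose a score, form a summary, or run the test nine times, and it does none of these explicitly. Taken literally, the sentence on continuous variables means one test per score.

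Two things are then at stake. First, the decision rule turns on statistical significance, yet for pain it cannot be applied, because nobody can say which score has to be significant. The choice could be made after the data are seen, by a team that Methods and Procedures says is not blinded. A chance difference at one early reading could be reported as a pain difference between the two procedures. Second, separate tests ignore that the scores come from the same patients. They are less precise than a single summary when the difference is sustained.

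The unreconciled schedules add to this. They leave open whether the first six hours belong to the pain endpoint at all.

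**Working it through.** **Plan's own figure.** The documents state no error rate for pain, so there is none to reproduce.

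**Inputs.** From the documents: 9 times (Methods and Procedures) or 3 (Study Design); 20 patients per cohort (Number of Subjects); alpha 0.05 and d = 0.6 (Data Analysis, which does not tie d to pain). Assumed: two-sided tests, and a within-patient correlation ρ that the documents do not give, shown from 0 to 0.9.

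**1. Schedules side by side.** Days 1, 2 and 7 correspond to 24 h, 48 h and 7 days. The six readings from 0.5 h to 6 h appear only in Methods and Procedures.

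**2. False positives if any significant time counts, with no true difference.** For independent scores the rate is 1 − (1 − 0.05)^k:
- k = 9: 1 − 0.95^9 = 0.370
- k = 3: 1 − 0.95^3 = 0.143

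For correlated scores (equal correlation, 20 per group, two-sample t-tests, 20,000 simulated trials per setting):

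| ρ | nine times | three times |
|---|---|---|
| 0.3 | 0.33 | 0.14 |
| 0.5 | 0.28 | 0.13 |
| 0.7 | 0.21 | 0.11 |
| 0.8 | 0.17 | 0.10 |
| 0.9 | 0.12 to 0.13 | 0.08 to 0.09 |

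The two-value cells show the spread between repeated runs. If correlation instead decays between successive readings (first-order autoregressive), the nine-time rates are 0.33, 0.28 and 0.18 at 0.5, 0.7 and 0.9. Using the paired t-test that the plan names, with arbitrary pairing of patients, gives almost the same rates.

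**3. One summary tested once.** In the same simulations, a single test of each patient's mean score had a false-positive rate of 4.8% to 5.3%, which is the nominal 5%. A Bonferroni correction would instead need 0.05/9 = 0.0056 per time, or 0.05/3 = 0.0167 for three.

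**4. Precision, illustrated with a constant d = 0.6 at every time and 20 per group.** Power for one time point is 0.46.

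The unweighted mean of nine scores has variance (1 + 8ρ)/9 relative to a single score. At ρ = 0.5 this is 5/9 = 0.556, so the effective d is 0.6/√0.556 = 0.805.

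For the trapezoidal area under the curve from 0.5 h to 168 h, the intervals are 0.5, 0.5, 0.5, 2, 2, 18, 24 and 120 h, total 167.5 h.
- Weight at 48 h: (24 + 120)/2 ÷ 167.5 = 0.430
- Weight at day 7: (120/2) ÷ 167.5 = 0.358
- Together 0.79. The six readings up to 6 h carry 14.5/167.5 = 0.09.
- The squared weights sum to 0.333, so the relative variance is ρ + (1 − ρ) × 0.333. At ρ = 0.5 this is 0.666, so the effective d is 0.6/√0.666 = 0.735.

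| ρ | mean of nine: variance, power | area under curve: variance, power |
|---|---|---|
| 0.5 | 0.556, 0.70 | 0.666, 0.62 |
| 0.7 | 0.733, 0.58 | 0.800, 0.54 |
| 0.9 | 0.911, 0.49 | 0.933, 0.48 |

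**The case against.** The strongest reply is that the plan never says all nine scores will be tested, nor that one significant score is enough. A reader might infer from the nine readings and the simple tests that the pain result has a 37% false-positive rate. The documents do not support that. With one time point fixed in advance the rate would be 5%. The only decision rule speaks of the endpoints being significant, which leans towards requiring all of them rather than any one. And 37% needs independent scores, which is implausible for readings from one patient, some of them 30 minutes apart. This stands: the inflation follows from an undefined endpoint, and is conditional.

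A reader might also infer that the two schedules contradict each other. They overlap, and Study Design does not say that its three days are the only ones, so it may be a shortened list. That stands too, but the protocol still has to say which scores form the endpoint.

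Third, the gain in power from a summary is easily overstated. It rests on an effect constant from 30 minutes to 7 days, which nothing in the documents supports. It is smaller for an area under the curve than for a plain mean, and nearly disappears at high correlation. Naming one time point would also control the error rate. All of this is fair, so the main reason for the change is a defined result, with precision a lesser benefit.

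None of these replies identifies the pain result that the plan intends to report.

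**Conclusion.** The point holds as a defect in a secondary endpoint. The plan collects up to nine pain scores, names only per-variable two-group tests, and makes conclusions depend on significance without saying which pain score counts.

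Its size depends on how the gap is filled. If every time is tested at 0.05 and any hit is reported as a pain difference, the false-positive rate is about 12% to 37% with nine times and about 8% to 14% with three, for assumed correlations from 0.9 down to 0. Every case in that range exceeds 5%. If one measure is fixed beforehand, there is no inflation.

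The primary blood-loss comparison is not touched by the number of pain readings. The label paired is wrong for two independent cohorts, but it does not drive these figures.

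**What to change.** 1. Reconcile Study Design with Methods and Procedures, so that both list the same pain times.
2. In Data Analysis, replace the separate tests with one prespecified pain comparison between independent cohorts, tested once at 0.05. It could be the cohort effect from a single repeated-measures mixed model with time as a factor, or the mean or area-under-the-curve VAS over a stated window compared by an unpaired test.
3. State that this comparison is the pain result to which the significance rule refers.
4. Report the individual times descriptively, with confidence intervals.

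This costs a few sentences and needs no extra patients, visits or data. The drawback is that a difference confined to one time is diluted in a summary. The window also needs deliberate choice: a full-week area under the curve puts about 79% of its weight on the 48 h and day 7 scores and says little about the first hours.

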Data recorded from this study will be organized in RedCap and maintained on the department's secure password-protected research drive until the data are de-identified. Participant medical information will only be available to the principal investigator and research staff as necessary for data analysis. All patient health information will be de-identified and assigned a code. Information linking participants' names, social security numbers and medical record numbers will be stored in a secure location separate from the medical information. This information will be destroyed at study closure.

Adverse Event Reporting

Information about any breach of confidentiality will be documented in the electronic data collection system and/or on the paper CRFs, as appropriate. It will be the responsibility of the Principal Investigator to report any Serious Adverse Event (SAE) that occurs during the data collection to the Institutional Review Board (IRB) within the timeframe specified by NYU SoM.

IV. RISK/BENEFIT ASSESSMENT

Risk

This study involves risk of medication side effects as well as a breech of confidentiality.

Intravenous TXA can cause the following side effects:

- Anxiety
- blurred vision
- changes in vision
- chest pain
- confusion
- cough
- dizziness or lightheadedness
- fainting
- fast heartbeat
- greatly increased or decreased frequency of urination or amount of urine
- increased thirst
- loss of appetite
- nausea or vomiting

- numbness of the hands
- pain, redness, or swelling in the arm or leg
- sudden shortness of breath or troubled breathing

Rare side effects include:

- Convulsions or seizures
- Orthostatic hypotension
- sweating
- trouble seeing
- unusual tiredness or weakness.

Protection against Risks

The patients will stay in the recovery unit a minimum of 3 hours after surgery as the mean duration of the effect of TXA is 3 hours and be monitored by the recovery unit nurses^{15,16}. Patients will be instructed to call the principal investigator and visit the emergency department if there are any symptoms of calf swelling or chest pain within the first seven days following surgery.

All patients will be de-identified and given a code. Information linking the patient codes to the participants' names and medical record numbers will be stored in a secure location separate from the medical information. Access to the information linking the linkage codes with participant identifiers shall be restricted.

Potential Benefits to the Subjects

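### Systematic side-effect recording covers five symptoms for 24 hours and omits the seizures, vision problems, calf swelling and chest pain named elsewhere; no method or window is stated for eliciting those later

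*Combined protocol and SAP*

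**What the plan says.** Safety appears in five places in the combined protocol and SAP.

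- **Rationale (Section I), hypothesis:** "We hypothesize that administration of TXA will reduce perioperative bleeding in osteotomy procedure with minimal side effects". No rate or threshold is given for minimal.
- **Methods and Procedures (Section III), recorded side effects:** "Incidence of TXA-related side effects (nausea/vomiting, itching, anxiety, increased thirst, rapid heartbeat) in the first 24 hours will be noted". The same section keeps patients in the study for one week, up to the first follow-up visit.
- **Analysis and Data Monitoring (Section III):** "Adverse events will be defined as negative reactions to the intravenous TXA during or after surgery, including seizures, vision problems". The principal investigator reviews accumulated data quarterly, including "If there were any adverse events, and if so were addressed appropriately and per protocol". There is also a stopping rule: "The study will be stopped if there are unexpected severe AE's in more than one patient". Safety summaries are submitted annually.
- **Adverse Event Reporting (Section III):** any SAE arising during data collection goes to the IRB. Documentation in the electronic system or on paper forms is specified for confidentiality breaches; no matching sentence covers clinical adverse events.
- **Risk and Protection against Risks (Section IV):** a list of possible TXA side effects, and an instruction to call the principal investigator and go to the emergency department "if there are any symptoms of calf swelling or chest pain within the first seven days following surgery".

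The objectives concern blood loss, pain and swelling. The statistical endpoints in Data Analysis are the same three.

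**The concern.** The one passage that says what is recorded, and when, does not match the events the protocol highlights elsewhere. Followed as written, it yields an incidence for five symptoms on the first day. For seizures, vision problems and possible clot symptoms, no question, visit or window is stated.

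Every patient receives an antifibrinolytic, and the hypothesis includes a statement about side effects. A report built on the 24-hour list could show few or no events of concern, and a reader could not tell whether none occurred or none were asked about. The quarterly review and the stopping rule work from the same captured data, so they too depend on how completely events are elicited.

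**Working it through.** The documents give no figure for safety, so there is none to reproduce. The check sets the sections side by side and then asks how much a complete record could show.

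**1. Lists compared**

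| Event | 24-hour list (Methods and Procedures) | Adverse event definition | Seven-day patient instruction |
|---|---|---|---|
| Five listed symptoms | yes | not named | no |
| Seizures | no | named | no |
| Vision problems | no | named | no |
| Calf swelling | no | not named | yes |
| Chest pain | no | not named | yes |

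None of the four event types in the lower rows (0 of 4) is on the recorded list. The Risk section lists 16 side effects plus 5 rare ones, 21 in all. The 24-hour list matches 4 of these (anxiety, heartbeat, thirst, nausea or vomiting). Its fifth item, itching, is not among the 21.

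**2. Time covered**

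Follow-up is 7 × 24 = 168 hours. The recorded window is 24 hours, and 24/168 = 14.3%.

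**3. What the other provisions add**

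- The adverse event definition has no 24-hour limit, but an event must be a reaction to TXA to count. A clot or a swollen leg after osteotomy that is put down to the surgery could fall outside it.
- Quarterly review and the stopping rule act on events already captured; neither says how events are found.
- SAE reporting does not cover non-serious symptoms, and no incidence by cohort is planned from it.
- The seven-day instruction relies on the patient calling. The protocol does not say that the report becomes a recorded outcome.

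**4. What complete capture could show**

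With 0 events in n patients, the exact upper 95% limit is 1 − 0.05^(1/n) one-sided and 1 − 0.025^(1/n) for a two-sided interval. The planned n is 40, or 20 per cohort (Number of Subjects). Data Analysis allows for losing 5 per group, which would leave 30, or 15 per cohort.

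| n | One-sided upper limit | Two-sided upper limit |
|---|---|---|
| 40 | 7.2% | 8.8% |
| 30 | 9.5% | 11.6% |
| 20 | 13.9% | 16.8% |
| 15 | 18.1% | 21.8% |

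The chance of seeing at least one event in 40 is 1 − (1 − p)^40. The documents give no event rates, so p is an assumed range:

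| Assumed true rate p | Chance of at least one event in 40 |
|---|---|
| 0.1% | 3.9% |
| 0.5% | 18.2% |
| 1% | 33.1% |
| 2% | 55.4% |
| 5% | 87.1% |

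Even perfect collection would therefore leave uncommon events largely unaddressed.

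**The case against.** The strongest reply is that the 24-hour list is not the whole safety system. Seizures and vision problems are adverse events by definition, with no time limit. The Risk section lists chest pain, limb swelling and vision changes as TXA effects, so these can count as adverse events even when not serious. The investigator reviews adverse events quarterly and is also the person patients are told to call. Recovery-unit nurses monitor patients for at least 3 hours. Since the protocol gives the mean TXA effect as 3 hours, a 24-hour window is defensible for acute drug symptoms. Safety is in neither objective and is not a statistical endpoint.

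All of this stands, and it rules out several stronger readings that a reader might infer:

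- **That the five symptoms are the only safety data, or that the other events would never be collected.** The adverse event definition, review, stopping rule and SAE reporting all presuppose some capture.
- **That no form field exists for patients' reports.** The case report form is not in the documents. The protocol is silent on such a field, which does not show that there is none.
- **That the protocol classes the omitted events as serious, or that every patient attends at one week.** It calls seizures and vision problems adverse events without grading them, and it allows for loss to follow-up.
- **That the short list is why the hypothesis cannot be supported.** The lack of an untreated group, the undefined threshold and the 40 patients limit any safety conclusion, whatever the list contains.

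The reply does not supply a stated method or window for eliciting the named events after 24 hours, and it does not explain why the recorded list and the other sections differ.

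**Conclusion.** The point holds as a mismatch between sections. Systematic recording is stated for five symptoms over 14% of follow-up. The four event types named in the adverse event definition and the patient instruction are absent from it, and thromboembolic events are not a named recorded outcome. The planned side-effect incidence would be incomplete for the hypothesis.

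This rests on reading the protocol text as the full statement of what is collected; a case report form with wider fields would reduce the gap. The 14% describes the recorded side-effect list and should not be read as the share of all safety surveillance.

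The primary blood-loss comparison is unaffected. The change is worth making because it is cheap and resolves an inconsistency, but it would not turn the study into a test of TXA safety. With no events in 40 patients, true rates up to 7.2% (one-sided) would remain compatible with the data, and up to 13.9% within a cohort of 20. Both cohorts receive TXA, so a difference between them would not isolate a drug effect.

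**What to change.** Reconcile Methods and Procedures, Analysis and Data Monitoring, Adverse Event Reporting and Protection against Risks so that they refer to one list and one window.

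- Use one fixed checklist, completed through the existing one-week visit. It should hold at least the current five items plus seizures, vision problems, calf swelling and chest pain. Name thromboembolic events as a recorded outcome. The sponsor can decide whether to add the remaining items of the Risk section.
- Keep the first-24-hour record as a separate time point if acute symptoms are of interest.
- Record each event with its date regardless of attribution to TXA, and enter attribution in a separate field. State that reports made by patients who call are entered on the same form.
- Report the number of patients with each event, overall and by cohort, with exact 95% confidence intervals. Use patients with a completed checklist as the denominator, so that a missed visit is not counted as no event.
- State that the safety results are descriptive, because there is no untreated group and the limits above are wide.

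This adds no visit and changes no treatment, monitoring or stopping provision. The cost is a few extra case report form fields and minor data entry.

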The total number of subjects enrolled will be approximately forty (40) patients, with 20 patients in the HTO cohort and 20 patients in the TTO cohort, calculated by post hoc analysis. The Patients will be recruited from routine clinical practice at The NYU Langone Health, Langone Orthopedic Hospital, Sports Medicine Division.

Gender of Subjects

Men and women will be included in this study.

Age of Subjects

Subjects included study will be at least 18 years of age.

Racial and Ethnic Origin

There are no enrollment restrictions based on race or ethnic origin.

Inclusion Criteria

Patients will be screened for eligibility using the following criteria. All study subjects must meet the following inclusion criteria:

- Patients undergoing a high tibial osteotomy (HTO)
- Patients undergoing tibial tubercle osteotomy (TTO) with or without medial patello-femoral ligament (MPFL) reconstruction
- Patients ages 18-60, inclusive

Exclusion Criteria

Patients meeting the following criteria will be excluded from participation in this study:

- Legally incompetent or mentally impaired (e.g., minors, Alzheimer's subjects, dementia, etc.)
- Younger than 18 years of age
- Older than 60 years of age
- Any patient considered a vulnerable subject including: pregnant women or fetuses, children, cognitively impaired adults, prisoners
- history of coagulation abnormalities and thromboembolic disease or current abnormal coagulation test values
- history of stroke or acute coronary syndromes within 3 months before surgery
- Preoperative (chronic) anticoagulation therapy
- Abnormal coagulation profile
- Renal failure (serum creatinine $> 250 \mu\text{mol/L}$ [2.83 mg/dL]) or liver cirrhosis
- Sickle cell disease
- Patients with a history of hypersensitivity to Percocet and/or TXA

Vulnerable Subjects

We do not intend to enroll vulnerable subjects.

Subject withdrawal criteria. Patients are free to withdraw at any time from the study.

III. METHODS AND PROCEDURES

Methods and Procedures

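### An adverse event counts only if it is first attributed to TXA, and a design in which every patient receives TXA cannot inform that attribution

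*Combined protocol and SAP*

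**What the plan says.** In section III, Analysis and Data Monitoring, the definition reads: "Adverse events will be defined as negative reactions to the intravenous TXA during or after surgery, including seizures, vision problems". The sentence before it is the protocol's only stopping rule: "The study will be stopped if there are unexpected severe AE's in more than one patient". Item 3 of the principal investigator's quarterly review, in the same section, also turns on whether there were adverse events. No broader definition appears elsewhere.

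On exposure, Methods and Procedures says "Patients will be given 1 gram of intravenous tranexamic acid (TXA) before tourniquet inflation and 1 gram of IV TXA before closure of the incision", and this applies to both cohorts. It adds "All patients will receive a standardized regimen of aspirin for DVT prophylaxis and Percocet for pain management". The cohorts differ by operation, not by drug: "Patients will be assigned to their cohorts based on diagnosis and appropriate treatment as determined by the surgeon".

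On recording, Methods and Procedures says "Incidence of TXA-related side effects (nausea/vomiting, itching, anxiety, increased thirst, rapid heartbeat) in the first 24 hours will be noted". Adverse Event Reporting says "Information about any breach of confidentiality will be documented in the electronic data collection system and/or on the paper CRFs, as appropriate". It then makes the principal investigator responsible for reporting any serious adverse event (SAE) to the IRB, with no limit by cause. Section IV lists chest pain, limb pain or swelling and sudden breathlessness among the possible effects of intravenous TXA. It also tells patients to call and attend the emergency department for chest pain or calf swelling in the first seven days.

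**The concern.** A safety count should first record what happened and then judge why. Here the order is reversed: the judgement of cause decides whether the event exists as an adverse event at all. That would be a weakness in any trial. It matters more here because there is no untreated group, so an excess of events under TXA could never show itself as a difference between groups.

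Two things are at stake. The hypothesis in the Rationale is that TXA reduces bleeding with few side effects, and a count that omits events ascribed to surgery leans towards confirming the second half of it. The same count also feeds the stopping rule, so how readily the rule responds depends on an attribution that the study cannot check.

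**Working it through.** The plan states no event rate and no operating characteristic for its safety rule, so there is no figure to reproduce. The check is mainly a comparison of the text, followed by an illustration.

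**1. Does attribution decide what is counted?** Yes. The definition is limited to reactions to TXA, and the stopping rule and review item 3 both use the defined term. An event not judged a reaction to TXA is not an adverse event for either purpose.

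**2. Can the design inform the attribution?** No. All patients in both cohorts receive TXA, an osteotomy, aspirin and Percocet within a short period. The HTO versus TTO comparison contrasts operations and diagnoses, so it cannot separate a drug effect from an operation effect.

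**3. Does other text repair this?** Only in part.
- The SAE duty has no causal limit, but SAE is not defined. It could be read as a serious event within the causal definition of an adverse event, and nothing links it to the stopping rule.
- Patients are told to call about clot symptoms, but nothing says that these calls are recorded or counted.
- The Adverse Event Reporting section names confidentiality breaches as what is documented in the data system and does not say the same of clinical events.
- The 24-hour symptom list has no thrombotic item, and its label assigns the symptoms to TXA although every patient also takes an opioid.

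**4. Illustration of how the stopping count depends on attribution.** Inputs from the documents: n = 40 ("The total number of subjects enrolled will be approximately forty (40) patients, with 20 patients in the HTO cohort and 20 patients in the TTO"), and a count met at 2 or more patients. Assumed, because the documents give neither: p, the true proportion of patients with an unexpected severe event of any cause, from 1% to 10%; and f, the share of those events attributed to TXA, from 100% to 0%. With patients independent and q = p × f,

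P(2 or more) = 1 − (1 − q)^40 − 40 q (1 − q)^39.

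For p = 5% and f = 1, q = 0.05: 1 − 0.1285 − 0.2706 = 0.6009. For f = 0.5, q = 0.025, and the result is 0.2642.

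| p | f = 1 | f = 0.5 | f = 0.25 | f = 0.1 | f = 0 |
|---|---|---|---|---|---|
| 1% | 0.0607 | 0.0172 | 0.0046 | 0.0008 | 0 |
| 2% | 0.1905 | 0.0607 | 0.0172 | 0.0030 | 0 |
| 5% | 0.6009 | 0.2642 | 0.0892 | 0.0172 | 0 |
| 10% | 0.9195 | 0.6009 | 0.2642 | 0.0607 | 0 |

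At any true rate, the chance of meeting the count falls as fewer events are attributed to TXA, and it is zero if none are.

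**The case against.** The strongest reply is that the protocol does not let serious events vanish. Any SAE goes to the IRB whatever its cause. For clot symptoms in particular, the protocol's own risk list points towards TXA, so an investigator might well attribute them to the drug. This stands. A reader might infer that a clot ascribed to surgery would never be reported, or that clots would always be ascribed to surgery, and the documents support neither. What remains is that the SAE route does not change the definition or feed the stopping rule. An event accepted as a listed TXA effect could also be read as expected, and so miss the stopping count for that separate reason.

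A reader might also set 0 of 40 events (exact 95% interval 0 to 8.8%) against 2 of 40 (0.6 to 16.9%) as the size of the problem. The intervals are correct, but the contrast assumes that two events occur, that both are misattributed, and that both are severe and unexpected. None of this is in the documents.

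Nor does the lack of blinding carry the point. Everyone receives TXA, so blinding to cohort would not help anyone judge whether TXA was the cause.

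Three further replies have force. Review items 2 and 4 cover patient wellbeing and risk/benefit and are not limited to TXA reactions, so an excluded event leaves item 3 but not necessarily the whole review. Safety is not among the named statistical endpoints, so no planned efficacy comparison changes. The 24-hour list describes no case-by-case attribution. Its label, and the fact that itching is absent from the section IV list, are minor inconsistencies.

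**Conclusion.** The concern holds as a defect in a stated rule, not as a missing detail. The adverse event definition contains a causal filter, the filter governs both review item 3 and the stopping count, and the design offers no comparison to inform it. Any severe event put down to the operation falls outside the definition, so the bias in the safety conclusion runs towards no harm.

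Its size cannot be derived from the documents, because they give neither an event rate nor the share of events likely to be attributed to TXA. The probabilities in the table rest on assumed values of both and on independence between patients. They show how far the stopping count depends on attribution. They do not predict what will happen. The conclusion does not extend to saying that serious events would go unreported to the IRB.

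**What to change.** - **Analysis and Data Monitoring:** define an adverse event as any untoward medical occurrence from the first TXA dose to the one-week visit, whatever its suspected cause. Record suspected relatedness in a separate field that does not decide whether the event is counted.
- **Adverse Event Reporting:** define SAE, and state that clinical events, including patients' calls about chest pain or calf swelling, are documented in the study data system.
- **Methods and Procedures:** report the listed 24-hour symptoms as observed incidence, without attributing them to TXA.
- **Stopping rule:** reconcile it with the revised definition, the SAE text and the section IV risk list, with the sponsor stating which events count. The choice is the sponsor's.

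The cost is protocol wording and one additional case report form field. The reported event rate will be higher, because events due to surgery and Percocet are included. If the sponsor decides that such events count towards stopping, the rule may be reached more often: on the assumed rates above, all-cause counting gives about a 19% chance at 2% and 60% at 5%. The sponsor should weigh this when stating which events count. The change is best made before enrolment, since events not recorded at the time cannot be reliably recovered later.
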